12.2 Scientific Committee and other project structures

The Project Coordinators will be supported by the following structures.

12.2.3 National Coordinators

The National Coordinators will coordinate local investigators and stimulate recruitment and data collection in each country. They will also organize, when feasible, local investigators' meeting.

12.2.4 Scientific and Organizing Secretariat

The Contract Research Organization (CRO) of the study will be Docleader Ltd. located in Solbiate Arno (Varese), Italy. When requested, this company will assist the Promoter and Coordinators in all the scientific and practical aspects related to the study, e.g. protocol and appendices definition, organization of investigators' meeting, contacts with the investigators, data management and analysis, reporting, etc. (see Section 12.4)

12.3 Investigators

This multicenter international project will involve investigators from Hypertension Centers worldwide. Initially two countries will be involved in the studies (Italy and Russia).

Basic technical requirements for the inclusion of a center in the project will be:

- The availability in the facility of a BPLab ABPM monitor
- The ability to perform proper 24-hour ABPM
- The potential for providing and properly following-up the number of patients required by the protocol
- The availability of Internet connection, regular access to the web and human resources to upload ABPM and clinical data

The investigator will need to have a medium-high level of expertise in informatics.

Given the observational nature of the project, it will not foresee any costs for the doctors and health insurance system and will not cause implementation of additional diagnostic examinations or changes in the use of any specific class of antihypertensive drugs.

12.4 CRO

Upon request, the CRO of the project will assist the Promoter in some of the activities related to the study (e.g. protocol finalization and formatting, training of the investigators in the project procedures, data management and analysis, preparation of statistical reports, etc.)

The CRO will have the responsibility to take all the necessary measures to ensure proper conduct of the project regarding the ethical aspects, adherence to the protocol, and the integrity and validity of data recorded in the e-CRF.

13.0 ETHICS

13.1 Independent Ethics Committee or Institutional Review Board

The data collection can be started in each center only after approval or notification (depending on local laws) of the project protocol Independent Ethics Committees.

13.2 Subject information and consent

The investigator must obtain written informed consent from each patient (*Appendix 2*), before submitting him or her to any procedure of the project.

Each patient must provide written informed consent after receiving information and explanations about the

objectives, commitments, rights and responsibilities faced by his/her participation in the project. In particular, the patient must be informed:

- That this is a research project
- About the objectives of the project
- About the project procedures
- About the free and voluntary participation in the project, and the possibility to get more information on the project from the investigator in charge of the project
- That anonymity of the patient will be kept on the official documentation of the project
- About the methods for the processing of personal data

The information will be provided to the patient through an information sheet (*Appendix 2*) and verbally by the investigator.

The written informed consent of the patient should be documented on the appropriate form, which must be dated and signed by the subject. According to local laws, the patient might also be asked to sign a separate form for the processing of personal data. The patient who will not provide the written authorization will not participate in the project. In case of subjects legally incapable or with restriction, consent must be provided by the legal representative.

The original signed informed consent obtained from the patient will be retained by the investigator in the patient's file at the project center, while one copy will be delivered to the patient.

14.0 DATA MANAGEMENT

14.1 Electronic Case Report Form (e-CRF)

Data will be collected for each patient by an e-CRF located on a website. The e-CRF will allow the collection of the main demographic and clinical data including the patient's medical history and concomitant therapies. All data must accurately reflect the patients' view, or be an expression of their knowledge about their health.

The following data will be entered in the e-CRF, for each subject and visit:

- Age
- Gender
- Height
- Weight
- Ethnicity
- Superficial distance between jugulum and symphysis (surrogate of aortic length)
- Waist circumference
- Smoking status
- Alcohol drinking
- Coffee or tea drinking
- Dyslipidemia (yes/no and indication on treatment)
- Diabetes (yes/no and indication on treatment)
- Diagnosis of hypertension (yes/no and indication on treatment)
- Family history of premature CV disease
- Medical history, with particular regard to previous and/or concurrent CV diseases
- Office blood pressure and heart rate obtained in the same treatment condition as ABPM
- Left ventricular mass index (LVMI) at echocardiogram
- When available, diameter of the aorta (aortic annulus, root and sinotubular junction) and/or cardiac output, assessed by the echocardiogram
- Intima-media thickness (IMT) at carotid ultrasonography
- ECG (indication on left ventricular hypertrophy, Sokolow–Lyon and Cornell index)
- When available, ankle-brachial index

- Microalbuminuria and serum creatinine (calculation of estimated glomerular filtration rate - eGFR)
- When available, pulse wave velocity (PWV) augmentation index (AI) and central blood pressure taken during the office visit with a validated device different for BPLab Vasotens (e.g. Sphygmocor or Complior)

Access to the e-CRF will be granted through authentication with ID and password. The investigator will be responsible for the faithful transcription of the results of any laboratory or instrumental diagnostic tests. If changes have to be made to data, they will be overwritten with the correct ones. The system will keep record of the date and time of the corrections.

The data entered in the e-CRF will be stored in a database residing on a webserver. When entering data in the e-CRF the system will automatically check their congruence. A further data check will be made on the database in order to highlight missing data, or compilation errors, inconsistencies, protocol violations. The list of these errors will be discussed with the investigator, and appropriate changes agreed with him/her. The blood pressure and arterial stiffness measurements made with the BPLab blood pressure monitor will be uploaded electronically by the telemedicine system onto the e-CRF.

14.2 Project monitoring

Given its observational nature, no formal monitoring is foreseen for this project. However, electronic data verification could be done by the monitor and data manager, who will get in touch with the investigators, via e-mail, fax or phone, and when needed may ask the investigator to correct the erroneous data or complete missing data on the e-CRF.

Each investigator will be required to keep records of the project in a file located at the project center. The investigator is asked to keep a paper or computer file of the patients enrolled in the project, but also of those assessed but not included in the project.

The Promoter might eventually ask the CRO to visit the center and will thus have free access to the documentation of the project in order to:

- Check the progress of the project
- Verify adherence to the protocol procedures
- Discuss any problems
- Review the adequacy of the completion of the e-CRF and that its content complies with the source data (in this case the patient's personal data will still be kept confidential)

The verification of source documentation may also be made in the course of an audit by the Promoter in order to ensure the validity of the data, or during the inspection by the competent authorities, depending on local rules. Personal data of the patient will still be kept confidential.

14.3 Data quality control and assurance

The investigator agrees to participate in the project in full adherence to the present protocol and to verify and check that the information provided on the e-CRF is as precise and accurate as possible.

The procedures for data monitoring and verification will be ensured by the presence of logical checks and range (defined a priori) for the different variables and by automatic identification of inconsistencies by the software used to manage the database. The controls and related corrections can be made on the e-CRF directly by the investigator on the website.

15.0 INSURANCE

Because of its observational nature, this project does not require insurance, apart from that already required for normal clinical practice and available at each general practice's or specialist' office.

16.0 DISCONTINUATION OF THE PROJECT

The Promoter reserves the right to discontinue the project at any time. This decision will be communicated in writing to the investigator. Similarly, if the investigator decides to withdraw from the project he/she must give immediate written notice to the Promoter.

18.0 REPORTING

Detailed reports of the study results will be published, starting from the end of the first year of follow-up. The investigator agrees that the results of this study can be verified by national and/or international quality control authorities. To do so, if requested, the investigator must provide to these authorities all the information requested.

19.0 DATA ACCESS AND PUBLICATION POLICY

All unpublished material (for example the protocol and the e-CRF) provided to the investigator is confidential and cannot be disclosed in any way without the written approval of the Scientific Coordinators. All data and results and all intellectual property rights derived from the project are the property of the Promoter.

Any publication or oral presentation concerning the project, even when regarding partial results, must be approved and authorized by the Promoter.

At each point of the project each member of the Scientific Committee can propose the performance of an analysis based on the data contained in the registry. The draft of the analysis plan will be discussed among the Scientific Committee members and undergo the final approval by the Scientific Coordinators and the Steering Committee. The author of the proposal will coordinate the data analysis, which will be performed centrally.

The authors' list for each publication will include the proponent(s) (as the first authors), all members of the Steering Committee, and up to three people most directly involved in the performance of the study. The authors list will include the statement "on behalf of VASOTENS Investigators" and the complete list of Scientific Committee members and Investigators will be provided at the end of the paper. This policy may be modified in individual cases upon agreement of all interested sides.

20.0 PROTOCOL AMENDMENTS

This protocol and appendices form an integral part of this document.

After the protocol is negotiated and signed by the parties no modification can be made by the Promoter, nor by the Coordinators or by the investigators, without agreement among the parties. Any agreed changes will be ratified in writing by the Promoter and Coordinator and annexed to this protocol.

Any amendment will be reported to the Ethics Committee.

22.0 APPENDICES

Appendices to the protocol are provided apart.

Appendix 1 - Ambulatory blood pressure monitoring procedures

Appendix 2 - Patient information sheet and informed consent form

Appendix 3 - Investigator's approval page

## 1. INVESTIGATORS

An updated list of the Investigators, with their address and status will be periodically provided to Biotechmed by the Study Coordinator ([name]) and saved on Biotechmed's server. The study will start in each center only after official approval of the local Ethics Committee. The Investigator will receive the BPLab device (if not yet owned) directly by BPLab. Upon confirmation of the study approval the Coordinator will inform BPLab which will ship the device to the Investigator (without the software).

The coordinator will inform Biotechmed that the center is ready to be opened and will give information on study address and Principal Investigator.

Biotechmed will prepare the sheet with the credentials and send them to the Investigator by e-mail: the e-mail will clearly state that before using the device for the first time the Investigator needs to contact Biotechmed which will help downloading e-THOLOMEUS and explain how to program the device, download the data from the device and fill in the e-CRF with the clinical information.

A group called "GRUPPO\_VASOTENS 80000" will be created in the Tholomeus website and any Investigator will be named as 800 + its center code: e.g. 800 + 08 = 80008. The user's profile must be the same of ARTEMIS. Only "Cardiovascular diagnosis" (BPLab) and "CRF" modules must be activated.

## 2. DATA COLLECTION

Detailed study procedures and further information and details on the study are available in the study protocol.

Briefly, each center will enroll 100 patients from their pool of hypertensive patients. There are no specific inclusion criteria, except that:

- Patients must be at least 18 years-old
- Patients with frequent ectopic beats, including atrial fibrillation must be excluded
- Arm circumference must be at least 22 cm (appropriate cuff must be used in case of large arms)

Patients will be visited ideally at 6 month-intervals or once-a-year. During the visit they will be submitted to an ABPM and clinical data (see below) will be collected.

### 2.1 ABPM

The investigators must ensure that for any given patient and visit the ABPM is valid:

- Interval between measurement not less than 30 min
- At least 70% of expected readings
- At least 20 valid readings during the day
- At least 7 valid readings during the night

The device must always be programmed with clear indication of day-time and night-time starting time.

Special period is not managed. The (surrogate) length of the aorta must be entered in the system at the time of programming the device, by measuring the distance between jugulum and symphysis.

If .BPW files are available they can be uploaded on the website. These files must contain the information on the length of the aorta.

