9.1 Inclusion criteria

- Male and female subjects
- Age ≥ 18 years
- Subjects referred to routine diagnostic evaluation for hypertension or established hypertensive subjects
- ABPM performed for clinical reasons with a BPLab device
- The minimum validity requirements for inclusion of the ABPM in the study are:
 - Interval between measurements not exceeding 30 minutes
 - At least 70% of expected number of readings
 - At least 20 valid readings during the day-time and 7 during the night-time
- Availability of individual measurements for ABPM on a .bpw file (BPLab format) or data directly downloaded on the telemedicine platform of the study (see below)
- Availability of basic clinical information (as detailed in Section 14.1):
- Availability of a signed informed consent form

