10.0 PROJECT ACTIVITIES

10.1 Creation of research network and data collection

Data contained in existing electronic databases or data of newly enrolled subjects fulfilling the inclusion criteria will be uploaded/entered on the study website. These data will include ABPM measures (blood pressure and arterial stiffness) obtained with a BPLab device and clinical data. ABPM data will be provided as .bpw files or directly uploaded by linking the ABPM device to the website through a personal computer. 24-hour ambulatory blood pressure recordings will be done in accordance with the procedures described in the *Appendix 1*.

Data collection will be ensured by a dedicated web-based telemedicine platform, including an electronic case report form (e-CRF). ABPM data will be transmitted to the project website and analyzed in real-time with production of an electronic report sent by e-mail to the Investigator and available on the website. Only ambulatory blood pressure data collected with a BPLab monitor will be included in the system. The e-CRF will allow collection of patient's clinical data, such as family history, anthropometric data, habits, past and current diseases, therapies, office BP, and laboratory tests, including evaluation of target organ damage. More than one ABPM recording may be performed in the same patient if deemed necessary by the physician in charge. They will be uploaded in the telemedicine system and complemented by an update of clinical information, as mentioned above. The project does not involve any type of intervention related to the study and the physicians will manage the patients included in the registry according to the requirements of clinical practice and current guidelines. However, as recommended by current guidelines, each patient will be followed-up with visits occurring at regular intervals (ideally every 6 months, and not less than once a year). The physicians will also be free to use the ambulatory blood pressure data in the clinical management of the patients.

The telemedicine system will allow a) standardized and centralized data collection, b) data validation by experts and counselling to remote centers, c) setup and maintenance of the Registry.

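### SAP 2.1 reverses the protocol's ABPM interval criterion: 30 minutes is a minimum in the SAP and a maximum in the protocol, so the two agree only at exactly 30 minutes

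*SAP*

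**What the plan says.** The protocol gives the minimum validity requirements for an ambulatory recording twice, in the synopsis (4.0) and in section 9.1. In both places the interval requirement is "Interval between measurements not exceeding 30 minutes". The accompanying requirements are at least 70% of expected readings, at least 20 valid day-time readings and at least 7 valid night-time readings.

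SAP section 2.1 opens its own list with "The investigators must ensure that for any given patient and visit the ABPM is valid". The first item is "Interval between measurement not less than 30 min". The remaining items repeat the protocol's 70%, 20 and 7.

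SAP section 3 gives the quality criterion for the analysis. It repeats the 70%, 20 and 7 but says nothing about the interval.

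**The concern.** Two documents in force for the same registry state opposite rules for which recordings are valid. The SAP line is worded as an obligation on investigators for every patient and visit, and nothing else in the SAP corrects it. If a centre applied it, two errors could follow.

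- **Valid recordings lost.** A recording denser than one reading every 30 minutes meets the protocol and fails SAP 2.1. If it is turned away before upload, no check on the database can reveal the loss. Recordings already held in centres' databases are exposed too, because their interval is fixed.
- **Invalid recordings admitted.** A recording sparser than one reading every 30 minutes fails the protocol but can meet every condition in SAP 2.1 and SAP 3.

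All the ambulatory parameters in SAP section 3 come from these recordings: brachial and aortic pressure, PWV, AI, weighted SD and average real variability. They serve as exposures for organ damage and events, and as outcomes in the group comparisons of SAP 3.1. Average real variability is built from differences between consecutive readings, so it depends directly on their spacing.

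The wording could reach centres through training. SAP section 1 has the platform operator contact each investigator to "explain how to program the device, download the data from the device and fill in the e-CRF with the clinical information".

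**Working it through.** The plan gives no figure to reproduce. The check is which recordings each document accepts.

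**Inputs**
- Protocol synopsis and 9.1: interval ≤ 30 min.
- SAP 2.1, read literally: interval ≥ 30 min.
- Both documents: ≥ 70% of expected readings, ≥ 20 day, ≥ 7 night.
- SAP 3: the 70%, 20 and 7 conditions only.
- Assumed, because the documents give no day or night hours: a 16 h day and 8 h night, with a range of 14 to 18 h for the day. The intervals below are illustrations.

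**Step 1: overlap.** The sets {interval ≤ 30} and {interval ≥ 30} share one value, 30 min.

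**Step 2: uniform intervals over 24 h.** Expected readings = 1440 / interval. The 70% requirement is rounded up.

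| Interval (min) | Expected | 70% | Protocol interval rule | SAP 2.1 interval rule |
|---|---|---|---|---|
| 15 | 96 | 68 | met | not met |
| 20 | 72 | 51 | met | not met |
| 30 | 48 | 34 | met | met |
| 40 | 36 | 26 | not met | met |

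At 15 and 20 min a recording can satisfy protocol 9.1 and SAP 3 and fail SAP 2.1 on the interval line alone.

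**Step 3: the 40-minute recording.** The 20 + 7 = 27 minimum exceeds the 26 needed for 70%, so it binds: 27/36 = 75%. Expected day and night readings are 21 and 15 (14 h day), 24 and 12 (16 h), and 27 and 9 (18 h). The 20/7 minimum can be met in each case, so the recording can pass SAP 2.1 and SAP 3 while failing the protocol.

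**Step 4: how sparse a recording can be.** With all readings valid, the largest uniform interval that meets the SAP conditions is min(day minutes / 20, night minutes / 7):
- 14 h day: min(42.0, 85.7) = 42.0 min
- 16 h day: min(48.0, 68.6) = 48.0 min
- 18 h day: min(54.0, 51.4) = 51.4 min

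The limit peaks at 1440/27 = 53.3 min, for a day of 1440/81 = 17.8 h. The 20/7 minimum therefore caps the sparse recordings but still leaves a range above 30 min.

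**Step 5: different day and night intervals.**
- 15 min day, 30 min night: 64 + 16 = 80 expected for a 16 h day (56 + 20 = 76 at 14 h; 72 + 12 = 84 at 18 h). It can meet the protocol and fails SAP 2.1.
- 30 min day, 60 min night: 32 + 8 = 40 expected for a 16 h day, 28 needed. It can pass the SAP conditions for days of 14, 16 and 17 h and fails the protocol. At 18 h it has only 6 night readings and fails both.

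**The case against.** The best defence is that the protocol governs. SAP section 2, the parent of 2.1, presents itself as a summary and sends the reader to the protocol for procedures. Under protocol 10.1, "Data contained in existing electronic databases or data of newly enrolled subjects fulfilling the inclusion criteria will be uploaded/entered on the study website". Protocol 14.3 states that "The investigator agrees to participate in the project in full adherence to the present protocol", and protocol 20.0 that "no modification can be made by the Promoter, nor by the Coordinators or by the investigators, without agreement among the parties". This makes it less likely that the SAP line would be followed. It does not remove the conflict: there is no explicit precedence clause, and SAP 2.1 states its own rule in full.

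Second, the reversed rule is not an analysis filter, because SAP 3 has no interval line. No document says that centres receive the SAP, and the training described in SAP section 1 does not mention validity criteria. New recordings follow protocol Appendix 1, which is provided separately. All of this stands, and it is why the harm is conditional.

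Third, sparse recordings may be caught later. Protocol 14.1 says "A further data check will be made on the database in order to highlight missing data, or compilation errors, inconsistencies, protocol violations", and individual readings are stored, so intervals can be checked. That is fair, although no described check names the interval. Rejected dense recordings could also still be uploaded if the centre kept the file, but someone would first have to know of them.

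Fourth, a complete 40-minute recording has 36 readings, more than the 34 that both documents accept at 30 minutes. This also stands. The case against admitting it is that it breaks the protocol's criterion and changes the spacing of readings. It does not rest on a lower count.

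**Conclusion.** The contradiction is certain from the text. The two interval rules are opposites and share only the value 30 minutes. Followed literally, SAP 2.1 rejects 15- and 20-minute recordings that can satisfy the protocol. It can also admit uniform intervals above 30 minutes, up to 42 to 53.3 minutes depending on day length, which the protocol excludes. Those upper limits rest on an assumed day of 14 to 18 hours and on every reading being valid; the reversal itself rests on no assumption.

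The practical effect is unknown. It depends on whether the SAP wording reached centres and on the intervals actually programmed, neither of which the documents show. No effect on any estimate can be calculated. The point should be fixed because a validity rule is wrong as written in one of two current documents and correcting it is nearly free.

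**What to change.** - Reconcile the protocol synopsis and section 9.1 with SAP 2.1, so that both documents carry one interval rule. Say whether it applies to day and night separately, since the two periods may be programmed differently.
- Repeat that rule in the quality criterion of SAP section 3, so that the analysis set is filtered on it.
- Only if the SAP wording was used at a centre or in training: notify the centres, and tabulate stored recordings by interval (below 30, exactly 30, above 30 minutes). The table cannot show recordings rejected before upload, so ask those centres about them directly. The file of assessed but non-included patients (protocol 14.2) is a starting point, but the protocol does not say that it records reasons, and it would miss rejected repeat recordings from enrolled patients.

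The cost is a few words in SAP 2.1 and one line in SAP 3. The conditional follow-up adds one notice, one table from data already stored, and one query to the centres concerned.
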